**The Psychopathological Impact of the SARS-CoV-2 Epidemic on Subjects Suffering From
Mental Disorders: Data From ASST Monza**

The Impact of the COVID-19 (SARS-CoV-2 Disease) on Psychopathology

NCT04694482

Document date: **20/04/2021**

STUDY PROTOCOL

Study design and participants

This is an observational retrospective study involving subjects evaluated at three time points: T0, corresponding to the outbreak of the pandemic (January-February 2020); T1, that was the lockdown period (the so-called “phase I”, in March-April 2020); T2, corresponding to the reopening and restarting (the so-called “phase II”, in May-June 2020).

Outpatients (aged 18-65) were recruited at three mental health services of ASST Monza: Cesano Maderno, Monza and Brugherio. Subjects were interviewed during psychiatric visits from November 12th 2020 until January 31st 2020 and information were collected retrospectively for the purposes of the study.

Inclusion criteria for both patients and HC consisted of: (1) being 18-65 years old; (2) ability to comprehend the Italian language; (3) ability to understand and sign the written informed consent. An additional inclusion criterion for patients was having a diagnosis of SKZ, BD, major depressive disorder (MDD), anxiety disorders, OCD or PDs according to the Diagnostic and Statistical Manual of Mental Disorders – 5th edition (DSM 5 – APA, 2013) criteria. An additional inclusion criterion for HC was living in the same geographical area of patients.

Exclusion criteria (for both patients and HC) were: (1) severe mental retardation; (2) pregnancy or post-partum; (3) presence of medical conditions potentially contributing to psychiatric symptoms (e.g. multiple sclerosis or re-exacerbation of inflammatory diseases); (4) treatment with compounds potentially involved in the onset or worsening of psychiatric symptoms (e.g. corticosteroids); (5) being health care workers involved in the sanitary emergency. Moreover, relatives of patients were excluded as HC.

All participants signed informed consent after the nature of the procedures had been fully explained. Study procedures were reviewed and approved by the local accredited Medical Ethics

Review Committee (named “Brianza Ethic Committee”). The research project is conformed to the provisions of the latest version of the Declaration of Helsinki.

Assessment

Data were collected retrospectively from patients’ medical records or, in case they were lacking, by interviews to the patients or their relatives and caregivers. HC were asked to compile a questionnaire to collect the same data as patients. Information included demographic variables such as age, sex, educational level, occupational status and marital status, as well as clinical variables, such as family history of psychiatric disorders, lifetime substance misuse, substance poly-abuse 6 months before and 6 months after the pandemic, medical (co)-morbidity, medical poly-comorbidity, the presence of at least 2 COVID symptoms, and, for patients, diagnosis. The rating scales are routinely administered during patients’ visits.

Primary outcomes

- Brief Psychiatry Rating Scale (BPRS) at T0, T1, T2;
- Clinical Global Impression (CGI) severity subscale at T0, T1, T2; improvement subscale at T1 and T2;
- Hamilton Anxiety Rating Scale (HAM-A) at T0, T1, T2;
- Impact of Event Scale – Revised (IES-R) at T1 and T2.

These rating scales were administered to all patients. HC were asked to retrospectively fill in the IES-R items referring to T1 and T2.

Secondary outcomes

- Disability Scale (DISS) at T0, T1, T2;
- Positive and Negative Symptoms Scale (PANSS), collected for SKZ patients at T0, T1, T2;
- Hamilton Depression Rating Scale (HAM-D) and Montgomery and Åsberg Depression Rating

Scale (MADRS), collected for MDD and BD patients at T0, T1, T2;

- Young Mania Rating Scale (YMRS), collected for BD patients at T0, T1, T2;
- Yale-Brown Obsessive-Compulsive Scale (Y-BOCS), collected for OCD patients at T0, T1, T2.

STATISTICAL ANALYSIS PLAN

Descriptive analyses of the entire sample were performed. Patients were divided into 5 groups according to diagnosis (SKZ, BD, MDD, anxiety disorders or OCD, PDs); multivariate analyses of variance (MANOVAs) and chi-square tests were used to compare groups on quantitative and qualitative variables respectively.

Linear regression models, adjusted for repeated measures, were applied to examine whether the change over time in psychometric scores differed between diagnostic groups and, for IES-R, between patients and HC. In the models, psychometric scores were treated as dependent variables. The model included fixed effects of time and diagnosis. The Akaike information criterion (AIC) was used to select the appropriate statistical model. The unstructured variance-covariance matrix was used to account for repeated measures within each subject. The significance was set at $p < 0.05$.

Statistical Package for Social Sciences (SPSS) for Windows (version 26.0) was used as statistical program.

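### Patients are recruited after all three time points with no requirement of illness at T0, so disorders that began in March-June 2020 may be counted as worsening of existing ones

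*Combined protocol and SAP*

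**What the plan says.** All references are to the combined protocol and SAP.

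- **Time points** (Study design and participants). Baseline is "T0, corresponding to the outbreak of the pandemic (January-February 2020"). T1 is March-April 2020. The last point is "T2, corresponding to the reopening and restarting (the so-called “phase II”, in May-June 2020").
- **Entry** (same section). "Subjects were interviewed during psychiatric visits from November 12th 2020 until January 31st 2020 and information were collected retrospectively". As printed, the window closes before it opens.
- **Patient criterion** (same section). "An additional inclusion criterion for patients was having a diagnosis of SKZ, BD, major depressive disorder (MDD), anxiety disorders, OCD or PDs". No date of onset, duration of illness or attendance at T0 is attached to it.
- **Exclusions** (same section). There are five, beginning "Exclusion criteria (for both patients and HC) were: (1) severe mental retardation; (2) pregnancy or post-partum". None concerns onset or first contact after T0.
- **Data source** (Assessment). "Data were collected retrospectively from patients’ medical records or, in case they were lacking, by interviews to the patients or their relatives and caregivers".
- **Comparator** (Primary outcomes). Healthy controls supply only the IES-R, at T1 and T2.
- **Model** (Statistical analysis plan). The stated fixed effects are time and diagnosis, and the aim is to see whether change over time differs between diagnostic groups. No term, restriction or sensitivity analysis concerns onset date or care status at T0.

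**The concern.** The title promises the effect of the epidemic on people who already have a mental disorder. The sample is defined by something later: having a diagnosis and attending one of three services after T0, T1 and T2 had all passed. Someone whose disorder began between T0 and T2 meets the written criteria. That person was less ill at T0 than at T1 or T2 because of when the disorder started, so even a perfectly accurate T0 score gives a rise. Better measurement does not remove it.

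Two results are exposed. The time effect takes in these rises, and for BPRS, CGI severity, HAM-A and the secondary scales there is no control group to show how much change to expect without an epidemic. The comparison of diagnostic groups is affected if the new cases are spread unevenly. It is plausible, though not stated in the documents, that recent onset is commoner in anxiety disorders and MDD than in SKZ or PDs. Anxiety or depression could then appear to have worsened more simply because of who entered. IES-R has no T0 value and is not affected in this way.

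**Working it through.** The plan gives no sample size, SD, effect size or share of recent-onset patients, so there is no stated figure to reproduce. The first two steps use the text. The last two are illustrations on assumed inputs.

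**1. Timing.** T2 ends on 30 June 2020 and the first interview is on 12 November 2020: 31 + 31 + 30 + 31 + 12 = 135 days later. The printed end date, 31 January 2020, falls 286 days before the start. Read as 31 January 2021, the window lasts 18 + 31 + 31 = 80 days, which fits the retrospective collection of T1 and T2 and the document date of 20/04/2021.

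**2. Who passes the criteria.** Take a person with a first depressive episode in April 2020 who attends in December 2020. Age, language and consent can be met. The diagnosis criterion is met. No exclusion applies. There is no T0 chart, but lacking records may be replaced by interview, and no stated rule drops a patient without a T0 score. What this does to the T0-T2 course depends on onset:

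| Onset | Built-in rise from T0 |
|---|---|
| By end of February 2020 | None from new onset |
| March-April 2020 | From T1 |
| May-June 2020 | At T2 only |
| July 2020 or later | Essentially none |

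**3. Comparison of two diagnostic groups.** Assumptions: already-ill patients do not change; shares f1 and f2 of the two groups had onset between T0 and T2; these rise by D, in units of the SD of change; 100 patients per group; two-sided 5% z-test (the plan does not state sidedness).

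- False difference = (f1 - f2) x D.
- SE (a), if 1 SD is the overall SD of change: sqrt(2/100) = 0.141.
- SE (b), if 1 SD applies within the already-ill and the new-onset patients separately, so that mixing them adds variance: sqrt{[2 + f1(1-f1)D² + f2(1-f2)D²]/100}.

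For 30% against 5% with D = 1, SE (b) = sqrt[(1.21 + 1.0475)/100] = 0.150.

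| f1 vs f2 | D | False difference | Rejection, SE (a) | Rejection, SE (b) |
|---|---|---|---|---|
| 30% vs 5% | 1 SD | 0.25 SD | 42% | 38% |
| 20% vs 2% | 1 SD | 0.18 SD | 25% | 23% |
| 10% vs 2% | 0.5 SD | 0.04 SD | 6% | 6% |

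**4. Time effect in one sample.** With share f, built-in mean change = f x D and SD of change = sqrt[1 + f(1-f)D²]. For D = 1 SD, the probability of declaring a change when already-ill patients have none is:

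| f | Built-in change | N = 100 | N = 200 | N = 400 |
|---|---|---|---|---|
| 2% | 0.02 SD | 0.055 | 0.059 | 0.068 |
| 5% | 0.05 SD | 0.08 | 0.11 | 0.16 |
| 10% | 0.10 SD | 0.16 | 0.27 | 0.48 |
| 20% | 0.20 SD | 0.46 | 0.75 | 0.96 |

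At f = 0 the rate returns to 0.05.

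**The case against.** **The text may imply care at T0.** The design is introduced with "This is an observational retrospective study involving subjects evaluated at three time points", the Assessment section says the scales are routine at visits, and the primary outcomes section says they were given to all patients. The variables listed after the interview fallback are demographic and clinical, not scale scores. On that reading every patient has a visit-based T0 score and was already in care. This is a fair reading, and it is why the point says such patients may be included, not that they were. But it is a description and not an eligibility rule, and the fallback sentence does not exempt the scales.

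**First contact is not onset.** A patient first referred in spring 2020 may have had untreated symptoms for years and show no built-in rise. This stands. The relevant date is when the disorder began, and first contact is only a proxy.

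**Lockdown onset may itself be epidemic impact.** Some of it may be. Without a comparator it cannot be separated from ordinary onset, and it is a different quantity from worsening of an existing disorder. That argues for reporting it separately.

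**The size is assumed throughout.** This also stands. The higher rejection rates need large and unequal shares, and the mildest between-group case is barely distinguishable from 5%.

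**Conclusion.** The concern holds as a design risk of unknown size. As written, the plan can admit patients whose disorder began between T0 and T2, and it has no means of identifying them in the analysis. If they entered, their rise would be attributed to worsening of an existing disorder. If they are unevenly spread across diagnoses, the group comparison may be biased for every outcome with a T0 value: BPRS, CGI severity, HAM-A, DISS and the diagnosis-specific scales. Under the assumptions shown, false rejection between groups ranges from about 6% to about 38-42%. If few such patients entered, the effect is negligible.

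A reader might infer more, and the documents do not support it:

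- *That every patient who became ill after T0 brings built-in worsening.* Onset in, say, September 2020 meets the entry criteria but adds essentially nothing to the T0-T2 change.
- *That such patients were in fact enrolled and kept.* The documents leave this open.
- *That losing T0 patients before the window exaggerates worsening.* Those who improved and were discharged are missed, which pushes towards apparent worsening. Those who dropped out, died or were still in hospital are missed too, which may push the other way. A patient admitted in spring and back in outpatient follow-up by November can still enter. The net direction is unknown.

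The conclusion also rests on reading the window as November 2020 to January 2021.

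**What to change.** Recruitment is complete, so this calls for a dated analysis set, not a new eligibility criterion.

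1. Correct the printed end date of the interview window.
2. Record for each patient the date of onset or diagnosis and the date of first contact with the service.
3. Run the T0-T1-T2 change models in patients whose disorder was documented as present by 29 February 2020, shown by a dated record of diagnosis or care. Describe later-onset patients separately, and give the all-patient result as a sensitivity analysis.
4. State that conclusions apply to patients still in care in late 2020. Where service lists allow, report by diagnosis how many patients in care at T0 were not seen in the window. This discloses the loss of T0 patients but does not correct it.

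The cost is a date check, which will be harder where records are lacking, and a somewhat smaller n. Patients who were ill at T0 but undocumented leave the main model; the all-patient analysis shows whether that matters.

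### IES-R and CGI-improvement have no T0 value, so the stated change-over-time question covers only lockdown to reopening for them; the group difference at each visit should be the stated contrast

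*Combined protocol and SAP*

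**What the plan says.** The protocol sets three periods: T0 is the outbreak (January-February 2020), T1 the lockdown (March-April 2020) and T2 the reopening (May-June 2020).

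Under Primary outcomes, BPRS and HAM-A are listed at all three, as is the "Clinical Global Impression (CGI) severity subscale at T0, T1, T2". Two measures are not: the CGI "improvement subscale at T1 and T2", and the "Impact of Event Scale – Revised (IES-R) at T1 and T2". Patients receive all the primary scales. For controls the plan names one scale: "HC were asked to retrospectively fill in the IES-R items referring to T1 and T2". The visit against which CGI-improvement is rated is not given.

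The Statistical Analysis Plan describes one family of repeated-measures regressions, used to "examine whether the change over time in psychometric scores differed between diagnostic groups and, for IES-R, between patients and HC". On the outcome it says: "In the models, psychometric scores were treated as dependent variables". On the terms it says: "The model included fixed effects of time and diagnosis". It makes no separate provision for scales without a T0 value. Diagnosis is defined as five patient groups. MANOVAs are also planned to compare groups on quantitative variables, which are not listed.

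**The concern.** The study title is about the psychopathological impact of the epidemic. Where a scale has T0, change over time can describe that impact. Where it has only T1 and T2, the one within-subject change available is from lockdown to reopening, which describes recovery or persistence. A group that was hit harder and stayed worse would show no differential change. A group that was hit harder and partly recovered would show a change in its favour.

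This matters most for IES-R. It is the only outcome scale that HC complete, so the whole patient-versus-HC comparison of outcomes rests on it, and the SAP states that comparison as a difference in change. CGI-improvement has a further difficulty: each score is itself a rating of change, so its T1-to-T2 difference has no clear meaning until the reference visit is known.

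**Working it through.** The documents give no sample size, SD or effect size, so there is no planned figure to reproduce. The check has two parts.

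**1. Which contrasts exist**

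| Scale | Visits | Who | Change available |
|---|---|---|---|
| BPRS, HAM-A, CGI-severity | T0, T1, T2 | patients | from T0, and T1 to T2 |
| CGI-improvement | T1, T2 | patients | T1 to T2 only |
| IES-R | T1, T2 | patients and HC | T1 to T2 only |

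No outcome scale gives a change from T0 that can be compared between patients and HC.

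**2. What differential change and level each detect**

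Assumptions, none from the documents: two groups of n each (30, 50 or 100); SD 1 at both visits; within-subject correlation ρ from 0.5 to 0.9; higher score is worse; two-sided 0.05 (the SAP gives 0.05 without sidedness); normal approximation. Let g1 and g2 be the group gaps at T1 and T2.

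- Differential change: estimate g2 − g1, variance 4(1−ρ)/n.
- Average level over both visits: estimate (g1+g2)/2, variance (1+ρ)/n.
- Level at T1: estimate g1, variance 2/n.

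Power is approximately Φ(|estimate|/√variance − 1.96).

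*Sustained gap, g1 = g2 = 0.6.* Differential change = 0.6 − 0.6 = 0, so rejection is 5% at every n and ρ. For level at T1 with n = 50: 0.6/√(2/50) = 3.00, and Φ(3.00 − 1.96) = 0.85.

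| n per group | Differential change | Level at T1 | Average level (ρ 0.9 to 0.5) |
|---|---|---|---|
| 30 | 0.05 | 0.64 | 0.66 to 0.77 |
| 50 | 0.05 | 0.85 | 0.87 to 0.93 |
| 100 | 0.05 | 0.99 | 0.99 or more |

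With a gap of 0.5 SD, power at T1 is 0.49, 0.71 and 0.94 for n = 30, 50 and 100. Differential change stays at 0.05.

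*Narrowing gap, g1 = 0.6, g2 = 0.3.* Differential change = 0.3 − 0.6 = −0.3 SD, in favour of the group that is worse at both visits. Average level = (0.6 + 0.3)/2 = 0.45 SD, against that group.

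| n per group | Power for the −0.3 change (ρ 0.5 to 0.9) | Power for average level (ρ 0.9 to 0.5) |
|---|---|---|
| 30 | 0.21 to 0.74 | 0.43 to 0.52 |
| 50 | 0.32 to 0.92 | 0.64 to 0.74 |
| 100 | 0.56 to 0.997 | 0.90 to 0.96 |

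For CGI-improvement no scale anchors are needed. Two equal ratings, both on the worsening side, differ by zero. A T1-to-T2 difference of zero therefore cannot be read as no deterioration since T0.

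**The case against.** A reader might infer that these scales are tested on T1-to-T2 change alone and that the plan would report no difference under a sustained gap. The documents do not support that. The model has a diagnosis main effect, which compares average level over the available visits, and the MANOVAs may compare level too. Taken literally, the model has no group-by-time term at all, so its only between-group test is one of level. The 5% rate above belongs to the hypothesis that the SAP states, not to a term that it names. This stands for the five diagnostic groups. It helps less for patients versus HC, because no patient/HC term is written and the MANOVAs are described for the diagnostic groups.

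A reader might also infer that the CGI-improvement result will have the wrong sign. That requires each visit to be rated against the previous one. If both are rated against T0, the T1-to-T2 difference is an ordinary recovery contrast with the right sign. The documents do not say which applies, so only the missing reference visit can be held against the plan.

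Three further points are fair:

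- The absence of T0 is not itself a defect. CGI-improvement is a change rating by construction, and IES-R is tied to an event. CGI-improvement is also only one subscale of the CGI outcome, and BPRS, HAM-A and CGI-severity still give change from T0 in patients.
- Lockdown-to-reopening change is a legitimate question, and an exactly constant gap is a chosen case. The difficulty is that this change is the only stated question.
- A patient-HC gap at T1 is not a clean measure of impact, since without an earlier value it may partly reflect prior distress. This is a real limit on the proposed contrast.

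**Conclusion.** The concern holds in a limited form. For IES-R and CGI-improvement, the stated hypothesis can address only change between lockdown and reopening. That quantity is zero under a sustained gap, whatever the sample size, and favours the worse group under a narrowing one. These two statements follow from the visit schedule alone. The power figures rest on the assumed gaps, group sizes, correlations and equal SDs.

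Level is partly covered among diagnostic groups by the main effect, but it is not the declared question. For patients versus HC on IES-R, no level contrast is written down. The consequence is a mismatch between the stated question and the study's aim on the only outcome scale HC complete. It is not a failure of the primary analysis as a whole. The plan should be changed, at little cost.

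**What to change.** **IES-R.** Fit group (patient/HC in one model, diagnosis in the other), time and group-by-time, keeping the unstructured covariance. State the group differences at T1 and at T2 as the contrasts of interest, and label T1-to-T2 change as a recovery contrast. The interaction is needed because a model with main effects only forces the estimated group difference to be the same at both visits.

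**CGI-improvement.** State the reference visit. Report group means at T1 and at T2 separately, do not interpret their difference as change from T0, and let CGI-severity carry change from T0.

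**Cost.** One added model term, a few contrasts and some SAP wording, using data already listed. The SAP describes its analyses in the past tense, so if results have been seen, the new contrasts should be reported as post hoc. The report should also state that, without a T0 value, the IES-R gap cannot be fully separated from pre-existing differences in distress.

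### The stated model has time and diagnosis effects but no time-by-group term, so it cannot test whether change differs between groups

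*Combined protocol and SAP*

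**What the plan says.** In the Statistical Analysis Plan section, the repeated-measures models are said to "examine whether the change over time in psychometric scores differed between diagnostic groups and, for IES-R, between patients and HC". In these models "psychometric scores were treated as dependent variables", so the outcome is the score at each time point and not a change score. The fixed part is described in one sentence: "The model included fixed effects of time and diagnosis". The within-subject covariance is unstructured and significance is set at 0.05. The section also says: "The Akaike information criterion (AIC) was used to select the appropriate statistical model". It lists no candidate models. Neither the protocol nor the SAP names a time-by-diagnosis or time-by-patient/HC term.

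The SAP divides patients into five diagnostic groups. The Assessment section lists the data collected with the wording "and, for patients, diagnosis", so HC have no diagnosis. Of the primary scales the protocol says "These rating scales were administered to all patients". HC contribute to one scale only: "HC were asked to retrospectively fill in the IES-R items referring to T1 and T2". Among the secondary scales, HAM-D and MADRS were "collected for MDD and BD patients at T0, T1, T2". PANSS, YMRS and Y-BOCS were each collected in a single diagnosis. DISS is listed with no diagnosis restriction.

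**The concern.** A difference between groups in change over time is, by definition, a time-by-group contrast. A model with time and diagnosis as main effects has no such contrast and assumes parallel courses. Run as described, it returns a time effect (one change shared by all groups) and a diagnosis effect (a level difference shared by all time points). Neither answers the question the section sets.

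The practical risk is misreading. Diagnostic groups may well differ in level on scales such as BPRS. A significant diagnosis effect could then be reported as a different response to the pandemic when it shows only that one group scored higher throughout. For IES-R, a patient/HC difference in level would not show whether the course from T1 to T2 differed. The scales affected include all four listed as primary.

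**Working it through.** The plan states no figure to reproduce (no sample size, power or effect size), so the check is of what the stated model can estimate.

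**Inputs.** Five diagnostic groups (SAP). Three time points for BPRS, CGI severity, HAM-A, DISS, HAM-D and MADRS; two for IES-R and CGI improvement (Primary and Secondary outcomes). Two diagnoses for HAM-D and MADRS. HC on IES-R only.

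**Step 1: what the model implies.** Write the mean score in group g at time t as E(Y) = m + a_g + b_t. The change from T0 to T2 in group g is (m + a_g + b_2) − (m + a_g + b_0) = b_2 − b_0. The group term cancels, so change is the same in every group whatever the data or the covariance structure.

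**Step 2: how much is missing.** With G groups and T times there are G×T cell means. The main-effects model has 1 + (G−1) + (T−1) mean parameters. The shortfall is (G−1)(T−1), which is the interaction.

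| Scale | G × T | Cells | Main-effects parameters | Interaction df |
|---|---|---|---|---|
| BPRS, CGI severity, HAM-A; DISS if in all five groups | 5 × 3 | 15 | 7 | 8 |
| HAM-D, MADRS | 2 × 3 | 6 | 4 | 2 |
| IES-R across diagnoses; CGI improvement | 5 × 2 | 10 | 6 | 4 |
| IES-R, patients vs HC | 2 × 2 | 4 | 3 | 1 |
| IES-R, HC as sixth level | 6 × 2 | 12 | 7 | 5 |
| PANSS, YMRS, Y-BOCS | 1 × 3 | 3 | 3 | 0 |

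The ranks of the design matrices agree with these counts.

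**Step 3: numerical check.** The main-effects model was fitted to arbitrary cell means, weighting cells equally. In the 5 × 3 layout the true T0-to-T2 changes spanned 8.82 points across groups; the fitted changes spanned 0. For patients vs HC at two times, the true span was 10.55 and the fitted span 0.

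**Step 4: can the diagnosis effect stand in?** A simulation with assumed inputs (two groups of 100, two times, SD 1, correlation 0.5, two-sided 0.05, 4000 runs) gave these rejection rates:

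| Truth | Group main effect | Time-by-group |
|---|---|---|
| Constant 0.5 SD level difference, equal change | 98.6% | 5.0% |
| Difference moves from −0.25 to +0.25 SD | 5.0% | 94% |

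The two tests answer different questions. These rates illustrate that point and say nothing about this study's power.

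**Step 5: the IES-R factor.** Diagnosis has five levels, all of them patients. HC have no value on it, so the factor as defined cannot carry a patient/HC contrast unless HC is added as a level or a separate patient/HC factor is used. The SAP says neither.

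**Step 6: precision of the right estimate.** Let s² be the variance of an individual change and N the total number of patients. The pooled change has variance s²/N. With five equal groups, each group's change has variance 5s²/N, and a difference between two groups has 5s²/N + 5s²/N = 10s²/N. The SE ratio is √10 ≈ 3.2. Equal group sizes and variances are assumptions, as group sizes are not given.

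**The case against.** The best defence is that saying a model included two effects does not exclude others. The same paragraph poses the interaction question, so the authors may have fitted the interaction and shortened the description. That is plausible, and it limits the finding: a reader might infer that the analysis actually run was invalid, and the documents do not show that. The defect in the stated model remains, because nobody following the text would fit the term or know which test answers the question.

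A reader might also infer that AIC decided whether the interaction stayed, making the key test depend on the data. The SAP does not say what AIC chose between. The next sentence reports the covariance structure, which is an equally likely use. Nothing can be calculated from the documents about how often AIC would have retained the term.

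Three narrower objections stand in part:

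- HC as a sixth level is an ordinary possibility, so the IES-R coding is a smaller, supporting gap and does not mean the comparison was impossible.
- The sentence about administration to all patients refers to the primary scales, so the 8 df for DISS is conditional.
- CGI improvement already rates change, so its diagnosis effect does compare average rated change. Whether ratings diverge between T1 and T2 still needs a 4-df interaction, so it is not wholly outside the point.

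**Conclusion.** The point holds for the model as written and must be fixed. Fitted as described, the model forces equal change in every group and cannot test the section's own question for BPRS, CGI severity, HAM-A, IES-R, HAM-D and MADRS, nor for DISS if more than one group was assessed. The missing term has between 1 and 8 df, depending on the scale. This follows from the stated groups, time points and effects alone; only the illustrative simulation and the SE ratio rest on assumed inputs. PANSS, YMRS and Y-BOCS are unaffected, since each has one diagnosis. Confidence is high that the term is absent from the text. Whether it was absent from the analysis cannot be settled from these documents.

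**What to change.** State and fit time, group and time-by-group for every scale measured in more than one group. Name the joint time-by-group test at 0.05 as the test of differential change. Keep the term whatever its AIC, and say what AIC was used to choose.

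For IES-R, state the coding: either a patient/HC factor with its time interaction (1 df), with a patients-only model for the five diagnoses (4 df), or HC as a sixth level with a stated patients-versus-HC contrast in change. For CGI improvement, say that the diagnosis effect compares average rated change and that the 4-df interaction tests divergence between T1 and T2. State which groups DISS covers. Report between-group differences in change with 95% confidence intervals.

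If the interaction was already fitted, the cost is a wording correction. If not, it is one added term per multi-group model, the IES-R models, a rerun in the same software, and disclosure as post hoc, since the document is dated 20/04/2021 and describes the analyses in the past tense. No new data are needed. The statistical price is wider intervals: about 3.2 times the SE of the pooled change for a difference between two groups, under the assumptions given above.

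### The outcome models name no covariate, which leaves mainly the unmatched patient-versus-HC difference in IES-R level open to confounding by age, sex or education

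*Combined protocol and SAP*

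**What the plan says.** The Statistical Analysis Plan gives the purpose of the models as to "examine whether the change over time in psychometric scores differed between diagnostic groups and, for IES-R, between patients and HC". The terms it names are these: "The model included fixed effects of time and diagnosis". It names no covariate, weighting or stratification.

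Three other statements could be taken for adjustment:
- "Linear regression models, adjusted for repeated measures, were applied". Here the adjustment is for correlation within a subject.
- "The Akaike information criterion (AIC) was used to select the appropriate statistical model". No candidate models or candidate covariates are listed.
- "multivariate analyses of variance (MANOVAs) and chi-square tests were used to compare groups on quantitative and qualitative variables respectively". This follows directly on the division of patients into five diagnostic groups. It does not mention HC, and nothing links its results to the outcome models.

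Under Assessment, the variables needed for adjustment are listed: "Information included demographic variables such as age, sex, educational level, occupational status and marital status". They were sought from controls too: "HC were asked to compile a questionnaire to collect the same data as patients". Under Primary outcomes, the only scale that controls complete is IES-R: "HC were asked to retrospectively fill in the IES-R items referring to T1 and T2".

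Under Study design and participants, the study is described as observational and retrospective. HC share the patients' 18 to 65 age limits, language and consent requirements and exclusions. They must live in the same area and may not be relatives of patients. No matching is described.

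**The concern.** Shared eligibility criteria are restriction, not matching. Age can still differ between groups within 18 to 65, and neither sex nor education is restricted. If patients and HC differ on one of these and it is related to IES-R, the unadjusted group effect carries that difference as well as any effect of diagnosis.

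The patient-versus-HC IES-R comparison is the most exposed. With only T1 and T2 available, no T0 score can show whether the groups already differed. If the groups are unbalanced, the plan as written offers no result that would show whether the difference survives adjustment.

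**Working it through.** **No figure to reproduce.** The documents give no sample size, standard deviation, effect size or group characteristics. Everything below is illustration on assumed inputs. The 0.05 significance level comes from the plan; a two-sided test is assumed.

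**Assumed inputs.** 200 patients and 80 HC; outcome SD 1 within group; T1-T2 correlation ρ = 0.7 unless stated; one binary covariate whose prevalence differs by 0.15 to 0.30 between groups. Its effect on level is 0.3 to 0.5 SD. Where it also alters change, it does so by 0.1 to 0.2 SD. A false positive means rejecting when the covariate-adjusted contrast is zero.

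**Formulas.** Bias = covariate effect × imbalance. Rejection rate = P(|Z + bias/SE| > 1.96).

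**Patients versus HC, level at one time point.**
- Bias: 0.3 × 0.15 = 0.045 to 0.5 × 0.30 = 0.15 SD.
- SE = √(1/200 + 1/80) = 0.132.
- Bias/SE = 0.34 to 1.13, giving a rate of 0.063 to 0.205.
- With 100 patients and 40 HC, SE = 0.187 and the rate is 0.057 to 0.126.

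**Patients versus HC, level averaged over T1 and T2.** SE = 0.132 × √((1 + 0.7)/2) = 0.122; rate 0.066 to 0.233.

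**Patients versus HC, change from T1 to T2.**
- If the covariate effect is the same at both times, it cancels: bias 0, rate 0.05.
- If it also alters change: bias 0.1 × 0.15 = 0.015 to 0.2 × 0.30 = 0.06 SD, and SE = 0.132 × √(2(1 − ρ)).

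| ρ | SE | Rate |
|---|---|---|
| 0.5 | 0.132 | 0.052 to 0.074 |
| 0.7 | 0.102 | 0.052 to 0.090 |
| 0.8 | 0.084 | 0.054 to 0.111 |

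**Five diagnoses.** Take 40 per group, covariate prevalence evenly spaced over a range of 0.15 to 0.30, and an overall F test on 4 and 195 degrees of freedom. The squared deviations of prevalence sum to 0.0141 to 0.0563.
- Level: noncentrality 40 × 0.3² × 0.0141 = 0.051 to 40 × 0.5² × 0.0563 = 0.5625; rate 0.052 to 0.079.
- Change (variance 2(1 − 0.7) = 0.6): noncentrality 0.009 to 0.15; rate 0.050 to 0.057.

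**Does adjustment remove it?** In 20,000 simulated trials (200/80, ρ = 0.7, imbalance 0.30), the unadjusted and adjusted rates were:

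| Contrast | Unadjusted | Adjusted |
|---|---|---|
| Level at T1 | 0.193 | 0.050 |
| Mean of T1 and T2 | 0.219 | 0.050 |
| Change, constant covariate effect | 0.050 | 0.050 |
| Change, extra 0.2 SD | 0.086 | 0.051 |

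**Why covariate-by-time terms are needed.** In 60,000 runs with the extra 0.2 SD effect on change and imbalance 0.30, adding only the covariate main effect left a bias of 0.060 SD and a rate of 0.093 in the group-by-time test. Adding covariate-by-time brought these to 0.000 and 0.049.

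**Sensitivity to the inputs.** A second set-up used a continuous covariate differing by 0.2 to 0.8 SD, correlated 0.1 to 0.3 with the score, and 50 to 200 per group. For level averaged over T1 and T2 it gave biases of 0.02 to 0.24 SD and rates from 0.051 to 0.74. The direction is stable; the size depends wholly on what is assumed.

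**The case against.** The strongest reply is that the plan's only stated question is about change over time, where a fixed covariate with a constant effect cancels. On the figures above, that contrast and the five-diagnosis test are barely exposed. This stands, and it confines the point mainly to IES-R level. Level still cannot be set aside, because the plan names no group-by-time term and the one group effect it does name is a difference in level. That missing interaction is a separate gap.

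Second, an unadjusted difference is a valid answer to a descriptive question, and the documents make no explicit causal claim about diagnosis. This also stands. The risk lies in a patient-versus-HC difference being read as due to diagnosis with no adjusted result beside it.

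Third, the sentence on fixed effects does not say that only those terms were used, and AIC might have admitted covariates. The plan does not say so, and AIC ranks models by fit; it does not identify confounders. The plan also promises descriptive analyses of the whole sample, which might display group characteristics, but that is not adjustment.

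Fourth, every magnitude is assumed, and nothing shows that a zero adjusted difference between patients and HC is plausible. The rates therefore illustrate how exposed each contrast is; they do not predict this study's error.

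A reader might infer that the groups are in fact unbalanced, or that all the group comparisons are seriously biased. The documents support neither: they give no group characteristics, and the exposure differs sharply between contrasts.

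**Conclusion.** The point holds in limited form. The named fixed effects are time and diagnosis, in a study that is neither randomised nor described as matched and that sought age, sex and education from both sides. The main exposure is the patient-versus-HC difference in IES-R level. The change contrast is at risk only if a covariate also affects change, and the five-group comparison is little affected under the inputs assumed here. Whether any bias exists, and how large it is, cannot be told from the documents. This is a cheap improvement to the plan and does not show that its results are wrong.

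**What to change.** For IES-R, patients versus HC, report two models side by side: time, group and group-by-time; and the same model with age, sex, age-by-time and sex-by-time. Fix these covariates in advance of fitting and do not let AIC choose them. Show a further sensitivity result that adds educational level and its time interaction, kept separate because education may partly result from the disorder. The same age- and sex-adjusted model may be shown as a secondary check for scales compared between diagnostic groups. State how many participants are lost to missing covariates.

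The document is dated 20/04/2021 and written in the past tense. If the analysis has been run, label the adjusted models as added sensitivity analyses and state whether the conclusions change.

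**Cost.** No new data collection. For IES-R, with two time points, age and sex add 2 + 2 × 1 = 4 model terms; with education coded as one term the total is 3 + 3 × 1 = 6. For scales at three time points, age and sex add 2 + 2 × 2 = 6. Some re-analysis is likely, and participants with missing covariates drop out of the adjusted models; their number cannot be known from the documents.
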